## **Synopsis:**

**Protocol title:** Evaluating the effects of short-term B-cell depletion on long-term disease activity and immune tolerance in relapsing multiple sclerosis.

**Indication:** Relapsing multiple sclerosis (MS).

## **Objectives**

- To determine whether two courses of treatment with ocrelizumab is associated with long-term suppression of disease activity in people with highly active relapsing MS.
- To test if two courses of treatment with ocrelizumab corrects the B-cell tolerance defects in patients with relapsing MS.

**Study design:** Open-label intervention.

**Number of patients:** 10

**Target population:** Adult patients with relapsing MS

## **Inclusion criteria:**

- Age 18 years and older.
- Diagnosis of RRMS based on the latest revision of McDonald criteria
- At least two Gd-enhancing lesions on the brain or spinal cord MRI done in the prior three months
- Naïve to disease modifying therapies or using an injectable therapy (interferons or glatiramer acetate); or, if history of receiving natalizumab, fingolimod, dimethyl fumarate and teriflunomide, no exposure for past three months
- Expanded Disability Status Scale (EDSS) score at the time of screening =<3

## **Exclusion criteria:**

- Contraindication to treatment with anti-CD20 antibodies, including being seropositive for HBsAg or HIV antibody or T-spot (or Quantiferon-Gold) positive
- Ever received B-cell depleting antibodies (rituximab, ocrelizumab, ofatumumab), alemtuzumab, daclizumab, mitoxantrone or hematopoietic stem-cell transplant
- Female who are pregnant, nursing or unwilling to use contraception up to six months after the second course of the infusion (or 12 months after the first infusion)
- Treatment with steroids in the past 30 days
- Clinically unstable medical or psychiatric disorders at the time of screening that require acute treatment as determined by the PI

**Study duration:** 2.5 years after the last dose of B-cell depleting antibody, ocrelizumab.

**Description of study intervention:** Participants will receive two courses of treatment with ocrelizumab, an FDA-approved medication for treatment of relapsing MS. The ocrelizumab infusions will not be

Version: 2.0

Date: 3/8/2019

repeated after these two courses. Patient will be monitored for the return of clinical or MRI disease activity for at least 2.5 years after the last dose ocrelizumab. Immune cell phenotype and B-cell tolerance characteristics will be assessed before start of the treatment with ocrelizumab and 12-18 months after the second course of ocrelizumab infusion.

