## Investigational plan

### Study design

This is an open label, single-arm study of anti-CD20 antibody, ocrelizumab in people with relapsing MS. Patients who fulfill the eligibility criteria will undergo blood draw for collection of peripheral blood mononuclear cells (PBMC). Participants will receive two infusions of ocrelizumab (300 mg) two weeks apart and then six months later (one infusion of 600 mg of ocrelizumab), according to the medication label and the standard of care. Baseline brain, cervical and thoracic MRI will be obtained about 12 weeks after the first course of treatment. Participants will be followed with clinical visits at least twice a year (or more frequently, if needed) and brain MRI (every six months) and cervical and thoracic spine MRI, at least annually, up to two and a half years after the baseline MRI.

The trial design is depicted in the following diagram:

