#### Intervention

##### Investigational treatments

The intervention in this study is the two courses of infusions of ocrelizumab, an FDA approved medication for relapsing MS. The patients will receive ocrelizumab 300 mg IV infusion on days one and 15, according to the standard infusion protocols. The protocols include pre-medicating with acetaminophen 650 mg orally, diphenhydramine 50 mg orally and methylprednisolone 125 mg IV. The anti-CD20 antibody infusion will be repeated in six months (single infusion of ocrelizumab 600 mg). These infusions are standard of care and are done according to the medication label. However, the infusions will not be repeated after these two courses of infusion (the first two infusion of 300 mg ocrelizumab two weeks apart is considered one course and the infusion of 600 mg of ocrelizumab six months later is considered the second course).

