### Changes in the study visits and procedures due to response to the CIVD-19 pandemic:

Considering the recent events (March 2020) surrounding the COVID-19 pandemic and JHU response, and the fact that our study participants can be particularly vulnerable to the infection with the novel coronavirus, we will implement the following changes in our study protocol to reduce the immediate hazard to our participants related to the risk of exposure to COVID-19:

- Follow-up visits, including Month 3, Month 6, Month 12 Month 18, Month 24 and Month 30 in-person visits can be replaced with telemedicine visits with the study PI.
- The medical history, symptom evaluation and side effects assessment components of the study visits will be conducted through the telemedicine visits.
- The physical examination, vital signs assessment, neurological examination, OCT and research blood sample collection for future analysis will be paused temporarily, as they would require an in-person visit and would pose a risk to the participants and the staff. They will be resumed as soon as possible, after the resumption of normal research activities at the JHU.
- The NeuroQoL quality of life assessment will be delivered to participants electronically. Secure Redcap surveys will be sent to the participants' email address. Results will be printed and filed in the study binders as usual.

Version: 2.0

Date: 3/8/2019

- The blood work to assess and monitor safety and adverse effects of the therapy, including lymphocyte subset analysis, will continue to be ordered and results will be reviewed electronically by the PI.
- Infusions of ocrelizumab: Ocrelizumab may theoretically increase the risk of infection with the novel coronavirus. Delaying the ocrelizumab infusions will be determined on a case-by-case basis by the PI.
- MRI Procedures: MRI studies may be delayed because of the delays in the ocrelizumab infusions.

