**Screening visit:** PI or designee will explain the study consent to study participants, and the study visit assessments will occur after the study participants sign the consent form. Screening visit procedures include review of eligibility criteria, physical exam, neurological examination, collecting vitals, blood work for assessing eligibility (liver function tests, complete blood count, Hepatitis- B surface antigen, Hepatitis- B core antibody, HIV antibody, lymphocyte subset including CD19+ B-cells, total IgG and IgM and urine pregnancy test) and blood draw (for collecting PBMCs), and completion of Neuro-QoL adult item banks. Study participants will be enrolled into the study after the study physician confirms participants' eligibility to move forward with the study.

Obtaining the B-cell depleting antibody (ocrelizumab) and all the subsequent study visits and MRIs are part of routine and standard clinical care. If the B-cell depleting medication is not approved by the participants' insurance policy, the patient will be excluded from the study.

**MRI procedures:** MRI scans will be performed at one of the Hopkins Radiology facilities at 3T. Conventional T2/FLAIR/T1-weighted images as well as post-contrast T1-weighted images of the brain will be obtained at months 3 (baseline), 12, 18, 24 and 30. Conventional T2/STIR/T1-weighted images as well as post-contrast T1-weighted images of the cervical and thoracic spinal cord will be obtained at months 3 (baseline), 12 and 24. Similar to the standard of care, brain, cervical or thoracic spine MRIs may be done as needed if the patient develop symptoms that could be suggestive for an MS relapse (based on the evaluation by a study neurologist). The MRI scans will be read by an attending radiologist at Johns Hopkins University, and these readings will be used for making decisions regarding the presence of new T2 or Gd-enhancing lesions suggestive for re-emergence of the radiological disease activity.

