**Assessment of T and B-cell phenotypes and function at baseline and 18-24 months post-B-cell depletion**

The assessment T and B-cell phenotypes and function and analysis of the central and peripheral B-cell tolerance checkpoints, as well as measurement of cytokines will be done at Yale University. 30 milliliters of blood will be drawn from the participants before start of the treatment with ocrelizumab (at the screening visit) and 12 or 18 months after the second course of ocrelizumab infusion (month 18 or 24 of the study) and will be sent to Yale University for the analyses explained below.

We will investigate the T and B-cell phenotypes in the blood samples from the participants in the study, pre-treatment and after they repopulate their peripheral B-cells likely at either 18- or 24-months time points. We will follow the frequencies of  $CD3^+CD4^+CD25^{hi}CD127^{lo}FOXP3^+$  Tregs, circulating  $CD3^+CD4^+CXCR5^+PD-1^+$  Tfh cells increased in several autoimmune diseases, and other CD4+ and CD8+ naïve and memory T cell subpopulations. We will also assess the production of several cytokines including IL-2, IL-4, IL-6, IL\_10, IL-17, IL-21, IFN-gamma and TNF-alpha by Tregs and other T cell subsets after activating PBMCs with phorbol-12-myristate-13-acetate (PMA) and ionomycin for 4 hours in the presence of GolgiStop (BD Biosciences) and intracellular staining with specific monoclonal anti-cytokine antibodies as previously reported by our laboratory. Hence, we will determine if the abnormal production of IL-17 and IFN-gamma previously identified in Tregs from people with MS or their elevated Tfh frequencies are corrected after two courses of anti-B-cell deletion. In addition, we will assess *in vitro* the suppressive function of Tregs from people with MS before and after B-cell deletion. Indeed, Tregs from people with MS have been reported to display decreased suppressive function and we will therefore be able to determine if ocrelizumab can normalize Treg function and if this feature is associated with long-term disease suppression.

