**Data safety monitoring committee (DSMB):** DSMB is not required for a small study using a medication that is FDA-approved for the condition, however, we will have the following treatment stop and study termination rules:

**Treatment stop rules:** Stopping the study is equivalent to restarting the B-cell depleting antibody (i.e. ocrelizumab) or another DMT, if there is medical contraindication to the continued use of ocrelizumab (e.g. development of allergic or severe infusion reactions during the last infusion). The followings are the criteria for restarting the DMT (stopping the study).

1. A clinical relapse, affecting optic nerves (with worst visual acuity of 20/50 or less) or causing motor weakness, ataxia, bladder or bowel symptoms. Pseudo-relapses are not uncommon among patients with MS. When in doubt, the PI will use MRI (similar to the standard of care) to confirm development of new lesions corresponding to patient's symptoms (based on the possible localization of the symptoms).
2. Development of two new T2 hyperintense lesions or two gadolinium enhancing lesions on any MRI after the baseline MRI. The baseline MRI was defined the MRI that is obtained three months after the first ocrelizumab infusion.

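### The Synopsis commits to at least 2.5 years of follow-up after the last ocrelizumab dose, but scheduled visits and brain MRI stop 24 months after the last planned dose

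*Combined protocol and SAP*

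**What the plan says.** All places are in the combined protocol and SAP.

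- **Synopsis, study duration:** "2.5 years after the last dose of B-cell depleting antibody, ocrelizumab". The description of the intervention adds that participants are monitored for return of disease activity "for at least 2.5 years after the last dose ocrelizumab".
- **Investigational treatments:** after the first course, "The anti-CD20 antibody infusion will be repeated in six months", with no further planned infusion. The schedule of events places this second course at month 6.
- **Assessment of T and B-cell phenotypes:** the later blood sample is taken "12 or 18 months after the second course of ocrelizumab infusion (month 18 or 24 of the study").
- **Pandemic changes:** the visit list reads "Follow-up visits, including Month 3, Month 6, Month 12 Month 18, Month 24 and Month 30 in-person visits". The schedule of events has the same last visit.
- **MRI procedures:** "images of the brain will be obtained at months 3 (baseline), 12, 18, 24 and 30". Cervical and thoracic spine MRI is scheduled at months 3, 12 and 24 only.
- **Study design:** follow-up runs "up to two and a half years after the baseline MRI". The treatment stop rules define that baseline scan as "the MRI that is obtained three months after the first ocrelizumab infusion".
- **Specific aims, Aim 1:** a minimum of two and a half years, with no starting point named.

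**The concern.** The same length, 2.5 years, is attached to the last dose in the Synopsis, to the baseline MRI in Study design, and to nothing in Aim 1. The schedule fits only a count from the first infusion.

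The choice of anchor matters because the primary objective is long-term suppression of disease activity after two courses. Observation time after the last dose therefore limits any statement on durability. A reader relying on the Synopsis would credit the trial with at least 30 months of treatment-free observation when 24 are scheduled. Month 30 is also where the Kaplan-Meier curve for the primary endpoint is administratively cut off for patients without an event.

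**Working it through.** **Inputs**

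- Month 0 is the first-course infusion visit (schedule of events).
- The last planned dose is at month 6 (Investigational treatments; schedule of events).
- The baseline MRI is at month 3 (schedule of events; treatment stop rules).
- The last visit and last brain MRI are at month 30; the last scheduled spinal MRI is at month 24 (schedule of events; MRI procedures).
- The stated length is 2.5 years, or 30 months.

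**Check on the last planned dose.** The immunology section equates 12 or 18 months after the second course with month 18 or 24: 18 − 12 = 6 and 24 − 18 = 6. The contraception criterion equates six months after the second course with 12 months after the first infusion: 12 − 6 = 6. All sources agree on month 6.

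**Can the stated 2.5 years be reproduced from the schedule?** Scheduled follow-up = 30 − anchor month; month required = anchor month + 30.

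| Anchor | Month | Scheduled follow-up to month 30 | Month required for 2.5 years |
|---|---|---|---|
| First infusion | 0 | 30 months | 30 |
| Baseline MRI | 3 | 27 months | 33 |
| Last planned dose | 6 | 24 months | 36 |

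Only the first-infusion anchor gives 2.5 years. The Synopsis names the last dose.

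**Shortfall against the Synopsis.** 36 − 30 = 6 months; 6/30 = 20%.

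**Spinal MRI.** 24 − 6 = 18 months after the last planned dose.

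**Study design against the Synopsis.** The ceiling is 3 + 30 = month 33 and the Synopsis minimum is month 36. The maximum falls 36 − 33 = 3 months before the minimum, so both cannot be met. Month 30 itself respects the ceiling.

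**Sensitivity to day 15.** If the six months run from the second infusion of the first course, the last dose is at 6 + 14/30.44 = about month 6.5, and follow-up is about 23.5 months. If the baseline scan is also counted from day 15, the ceiling is 3 + 14/30.44 + 30 = about month 33.5, still before month 36. The conclusion does not change.

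**Separate check on brain MRI frequency.** Study design says every six months. The schedule has no brain MRI between months 3 and 12: 12 − 3 = 9 months.

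**The case against.** The strongest reply is that nothing in the planned analysis uses the Synopsis figure. The primary endpoint clock starts after the third month following the first infusion, not at the last dose. The Statistical analysis section plans a proportion and a Kaplan-Meier curve in 10 patients, with no test or landmark at 2.5 years after the last dose, and the sample size rationale does not use follow-up length. This stands, and it is why the effect is modest.

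It can also be said that the body of the protocol hangs together better than the Synopsis does. Aim 1 is met by month 30 if counted from the first infusion, and month 30 lies within the Study design ceiling. That makes a misplaced anchor in the Synopsis plausible, but does not establish it. The Rationale's mention of a three-year trial might be taken as support for month 36, but it appears in an argument about a hypothetical controlled design. The trial diagram, which the End of Study Definition relies on, could not be seen in the text available for this review. It may show which length is meant, but it cannot make the written sections agree.

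Two stronger readings are tempting, and the documents do not support them:

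- A reader might infer that every patient loses 20% of the information on the primary endpoint. In fact the shortfall matters only for patients still event-free at month 30; anyone who fails earlier already has an event time.
- A reader might infer that delayed second infusions, which the pandemic section allows, shorten post-dose follow-up further. The documents give no length of delay and do not say that visits stay fixed to the first infusion. The same section says MRI may be delayed along with the infusions. No figure can be put on this.

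As-needed visits and symptom-driven MRI do not answer the point, since they add no scheduled follow-up after month 30.

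**Conclusion.** The point holds. The Synopsis states a design property that the schedule does not deliver: at least 30 months after the last dose against 24 scheduled for visits and brain MRI, and 18 for scheduled spinal MRI. The Study design ceiling cannot be met together with the Synopsis minimum either.

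This rests on taking the last dose to be the second planned course at month 6, given on time, and on reading the visit months from the first infusion, as the schedule does. The consequence is confined to how far durability can be claimed for patients event-free at month 30. It does not invalidate the primary analysis or change any power figure. It should be fixed because it bears directly on the primary objective and correcting the wording is cheap. The nine-month brain MRI interval is a separate, minor inconsistency and adds no weight to this conclusion.

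**What to change.** Reconcile the Synopsis, Aim 1, Study design, the schedule of events, the pandemic visit list and MRI procedures to one anchor and one length.

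- **If the schedule stands:** restate the Synopsis as follow-up to month 30, that is, 2.5 years after the first infusion. Say that this is 24 months after the last planned infusion for visits and brain MRI, and 18 months for scheduled spinal MRI. Give Aim 1 and Study design the same anchor. Report each patient's actual follow-up after the last dose, and limit durability conclusions to what was observed.
- **If 2.5 years after the last dose is intended:** the sponsor must bring the schedule and the Study design ceiling into line with it. How to do so is for the sponsor to decide.

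The first route costs wording and one reported quantity per patient; its downside is a less favourable stated duration, 24 months after the last planned dose where at least 30 is now stated. The second needs a protocol amendment and assessments beyond month 30.

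Separately, reconcile the six-monthly brain MRI in Study design with the schedule of events and MRI procedures, which plan none between months 3 and 12.

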**Assessments:**

**The primary endpoint** (the failure event) of this study is the time to return of disease activity after the third month post-first-infusion, objectively demonstrated by development of new T2 hyperintense lesions or Gd-enhancing lesions on the MRI or a clinical relapse that is confirmed with an objective change in the neurological examination or a corresponding new or enhancing lesion on the MRI that is obtained after the onset of symptoms.

Mechanistic studies will be performed on the peripheral blood mononuclear cells obtained before the infusions and periodically after the infusions.

**Study locations:** This study will be conducted at Johns Hopkins University (JHU).

**Sample size and statistical analysis**

This is a pilot proof of concept study and no formal sample size calculations are performed.

We will recruit 10 patients in this study.

## Introduction

### Background and rational for performing this study

Disease modifying treatments and relapsing multiple sclerosis

Controlling and even stopping the inflammatory disease activity (i.e. clinical relapses and gadolinium enhancing or new T2 lesions on the MRI) is nowadays possible in most patients with relapsing forms of multiple sclerosis (MS). However, in most instances, it requires continuous and long-term treatment with a disease modifying treatment (DMT), which is costly, disruptive to the life of patients, associated with a sense of having a chronic disease and potentially adverse effects that are commonly seen with prolonged immunosuppressive therapies (opportunistic infections and cancers). To control the disease activity, almost all the available DMTs need to be used continuously. Stopping them is associated with return of the disease activity and in the case of two medications (fingolimod and natalizumab) with the possibility of more severe return of the disease activity compared to the pre-DMT baseline (rebound phenomenon).

There are currently two strategies that can result in medication-free prolonged freedom of disease activity in a proportion of patients: hematopoietic stem cell transplantation and treatment with alemtuzumab. Intense immunosuppression, followed by autologous bone marrow transplantation stopped the disease activity in more than 80% of patients with highly active relapsing MS. Two courses of treatment with anti-CD52 monoclonal antibody, alemtuzumab, have also been reported to be associated with prolonged freedom from clinical and radiological disease activity. In a report from 5 years of extension of the pivotal clinical trials of alemtuzumab in relapsing MS (CARE-MS studies), more than 60% of patients who only received two courses of alemtuzumab, did not need retreatment. However, both these approaches have high morbidity and are even associated with mortality, are reserved for cases with extremely severe disease and patients who have accumulated disability and their disease activity could not be controlled with other approaches.

In an ideal situation, a short course of treatment with a safe disease modifying therapy would have long-term or permanent effects on immune tolerance and stop the disease activity.

### B-cell depleting antibodies and relapsing MS

B-cell depleting anti-CD20 monoclonal antibodies, rituximab and ocrelizumab, have been shown to reduce the disease activity and using the most objective measure (Gd-enhancing lesions on the MRI), they effectively stop the disease. The short-term use of these medications has been safe and aside from preventable or manageable infusion reactions, no short-term serious side effects have been associated with them. However, based on the current practice and the medication label, these antibodies are supposed to be infused either every six months or at intervals trying to keep the peripheral blood depleted of B-cells. Long-term B-cell depletion has known and predictable side effects (such as hypogammaglobulinemia) and possible unpredictable adverse effects (e.g. increased risk of infection or cancer). For example, in two pivotal clinical trials of ocrelizumab in RRMS, the rate of upper respiratory infection and nasopharyngitis was mildly elevated, compared to the interferon beta-1a. However, across the clinical trials (in both RRMS and PPMS), the rate of developing the first neoplasm seemed to be twice as high as the comparator groups (0.4 per 100 patient-years of exposure versus 0.2 per 100 patient-years of exposure to other agents, including placebo and interferon beta-1a). It is conceivable that longer duration of exposure to these medications may be associated with increased number of cases

Version: 2.0

Date: 3/8/2019

experiencing serious side effects, including infections and perhaps cancer. Long-term use of these medications is also very costly. However, there is evidence that even short-term treatment with B-cell depleting agents can result in prolonged suppression of disease activity. For example, long term follow-up of patients who participated in a phase II clinical trial of ocrelizumab demonstrated that the relapse rate did not increase after the B-cell repopulation and only one patient in the ocrelizumab group had a Gd-enhancing lesion 18 months after the 4th and final ocrelizumab infusion, similar to the 12 month data following only one cycle of rituximab infusion in the phase two trial. Our colleagues have reported cessation of disease activity in four patients with neuromyelitis optica for a long period of time after they stopped treatment with rituximab. Based on these data and experiences, we believe that even a short course of treatment with anti-CD20, B-cell depleting antibodies can result in prolonged drug-treatment-free cessation of disease activity, at least in a subset of patients. With treatment with anti-CD20 therapies for a limited period (instead of long-term treatment), we probably avoid the side effects of prolonged lack of B-cells in the circulating blood. If a short course treatment with these medications has similar efficacy to continuous treatment, aside from lower probably of experiencing side effect, it puts much smaller financial burden on patients, their families and the health system. This strategy would put an end to the controversy of whether to start people with MS on a safe, but less efficacious medication (escalation approach) or on a potent, but with potential or unknown long-term side effects (induction approach). If temporary B-cell depletion stops the disease activity in a large proportion of patients, its safety and inexpensiveness allow us to use it almost universally in most people with MS. The next step would be trying to find biomarkers that might be associated with this long-term suppression of the disease activity.

